4.1 Inclusion criteria

Subjects must meet all the inclusion criteria to participate in this study.

- Laboratory confirmed SARS-CoV-2 infection
- Age ≥ 18 years
- Requires hospital admission for further clinical management
- Modified ISTH Overt DIC score ≥ 3

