5.2 Trial interventions

As standard of care, hospitalized patients with confirmed COVID-19 will be monitored for coagulopathy. Daily blood tests for platelet count, prothrombin time, D-Dimer, and fibrinogen and weekly thromboelastography will be obtained, and a daily Modified ISTH Overt DIC score will be calculated (Exhibit 1). Only patients meeting all inclusion and exclusion criteria will be asked to participate in the trial. Patients will be randomized to one of two arms:

- 1) Patients randomized to the **standard of care arm** will receive low-dose enoxaparin (40 mg subcutaneously daily if BMI <40 and 30 mg subcutaneously twice daily if BMI ≥ 40).
- 2) Patients randomized to the **intervention arm** will receive intermediate-dose enoxaparin (1 mg/kg Subcutaneously daily or 0.5 mg/kg Subcutaneously twice daily if BMI ≥ 40).

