It is expected that the IRB will have the proper representation and function in accordance with federally mandated regulations. The IRB should approve the consent form and protocol. In obtaining and documenting informed consent, the investigator should comply with the applicable regulatory requirement(s) and should adhere to Good Clinical Practice (GCP) and to ethical principles that have their origin in the Declaration of Helsinki. Before recruitment and enrollment onto this study, the patient will be given a full explanation of the study and will be

given the opportunity to review the consent form. Each consent form must include all the relevant elements currently required by the FDA Regulations and local or state regulations. Once this essential information has been provided to the patient and the investigator is assured that the patient understands the implications of participating in the study, the patient will be asked to give consent to participate in the study by signing an IRB-approved consent form. Prior to a patient's participation in the trial, the written informed consent form should be signed and personally dated by the patient or the patient's legally acceptable representative, and by the person who conducted the informed consent discussion.

10. Statistical analysis and considerations

The null hypothesis is that intermediate-dose LMWH (intervention arm) will have a mortality rate that is not less than low-dose LMWH (standard of care arm). A sample size of 82 patients to each arm of the study are needed to have 80% power when testing a difference of 20% (40% vs 20% for the two arms). Mean with SD and frequencies for all variables will be reported for each arm. A chi-square test will be conducted to test the mortality difference between the two arms.

Exhibit 1

Modified ISTH Overt DIC Score	
Laboratory Results	Points
Platelet Count	
> 100,000/ μ L	0
< 100,000/ μ L and \geq 50,000 / μ L	1
< 50,000 / μ L	2
D-Dimer	
No increase, \leq 0.50 mcg/mL	0
Moderate increase, >0.50 and <3.00 mcg/mL	2
Strong increase, \geq 3.00 mcg/mL	3
Prothrombin time	
Prolonged < 3 sec	0
Prolonged 3 to 5 sec	1
Prolonged \geq 6 sec	2
Fibrinogen level	
> 100 mg/dL	0
< 100 mg/dL	1
Interpretation of Score	

If \geq 3: compatible with COVID-19-associated coagulopathy
If $<$ 3: not suggestive of COVID-19-associated coagulopathy

References

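### Do the unscored values in Exhibit 1 leave the DIC-score entry criterion unreliable?

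*Combined protocol and SAP*

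**What the plan says.** Section 4.1 of the combined protocol and SAP makes "Modified ISTH Overt DIC score ≥ 3" an inclusion criterion. Section 5.2 says that "a daily Modified ISTH Overt DIC score will be calculated (Exhibit 1" is the source table.

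Exhibit 1, which follows section 10, sets these points:

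- **PT:** "Prolonged < 3 sec" scores 0, "Prolonged 3 to 5 sec" scores 1, and 6 seconds or more scores 2.
- **Platelets:** above 100,000/µL scores 0, from 50,000 to below 100,000 scores 1, below 50,000 scores 2.
- **Fibrinogen:** above 100 mg/dL scores 0, below 100 scores 1.
- **D-dimer:** up to 0.50 mcg/mL scores 0, "Moderate increase, >0.50 and <3.00 mcg/mL" scores 2, and 3.00 or more scores 3.

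The D-dimer bands meet without a gap. No rounding rule for PT is given.

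**The concern.** Three kinds of value have no row: PT prolongation above 5 and below 6 seconds, platelets of exactly 100,000, and fibrinogen of exactly 100 mg/dL. The threshold of 3 is low, so one point can decide entry. Two people scoring the same chart might disagree. If an unmatched PT were given no points, the rule would also run backwards: a patient with a longer PT could be turned away while one with a shorter PT was admitted. At stake would be a reproducible definition of the trial population. Because the score is calculated every day, the same ambiguity could recur.

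**Working it through.** **Inputs.** The Exhibit 1 points listed above and the entry rule in section 4.1. Score S = platelets + D-dimer + PT + fibrinogen points; eligible if S ≥ 3.

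**Step 1: the PT example.** Take D-dimer 1.5 mcg/mL (2 points), platelets 150,000 (0) and fibrinogen 400 mg/dL (0), so S = 2 + PT points.

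| PT prolongation | PT points | S | Eligible |
|---|---|---|---|
| 4.0 s | 1 | 3 | yes |
| 5.5 s, lower neighbouring row | 1 | 3 | yes |
| 5.5 s, upper neighbouring row | 2 | 4 | yes |
| 5.5 s, no points | 0 | 2 | no |
| 6.0 s | 2 | 4 | yes |

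Only the no-points reading makes the score fall. Exhibit 1 itself speaks against it, since 0 belongs to prolongation under 3 seconds. With either adjacent row the sequence is 3, 3, 4 or 3, 4, 4, and the patient enters.

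**Step 2: all combinations.** Counting each gap as its own category gives 4 platelet × 3 D-dimer × 4 PT × 3 fibrinogen = 144 combinations. Those without a gap number 3 × 3 × 3 × 2 = 54, leaving 144 − 54 = 90 with at least one. Each unscored value was given the points of each neighbouring row in turn (PT 1 or 2; platelets 0 or 1; fibrinogen 0 or 1). Eligibility changes in 17 of the 90:

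| D-dimer | Combinations that switch |
|---|---|
| ≤ 0.50 mcg/mL | 14 |
| > 0.50 and < 3.00 | 3 |
| ≥ 3.00 | 0 |

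- With D-dimer at 3.00 or more, S is already at least 3.
- The three moderate D-dimer combinations all have PT prolonged by less than 3 seconds, with platelets exactly 100,000, fibrinogen exactly 100, or both. With one boundary value, S is 2 + 0 = 2 or 2 + 1 = 3.
- Eight of the 17 need two or three unscored values in the same patient on the same day. The remaining 17 − 8 = 9 have a single one: PT in 2, platelets in 3, fibrinogen in 4.
- The two PT-only combinations have normal D-dimer plus one point from low fibrinogen or from platelets of 50,000 to below 100,000: S = 0 + 1 + 1 = 2 or 0 + 1 + 2 = 3.

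**Step 3: the no-points reading.** If every unscored value earned zero, 24 of the 90 would fall below 3 where a neighbouring row gives at least 3. Twelve of the 24 need more than one unscored value.

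**Step 4: use of the score after entry.** The holding rules in section 5.3 use platelets, fibrinogen and GFR directly. None of the outcomes in section 7.1 uses the score. The test in section 10 compares mortality. Section 6 has eligibility confirmed before allocation.

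**Step 5: the plan's sample size.** For 40% versus 20% with 80% power, assuming a two-sided 5% level (section 10 states neither level nor sidedness) and no continuity correction:

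n = [1.960 √(2 × 0.30 × 0.70) + 0.842 √(0.40 × 0.60 + 0.20 × 0.80)]² / 0.20² = (1.270 + 0.532)² / 0.04 ≈ 81.2, rounded up to 82 per arm.

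The plan's figure is reproduced, and the score does not enter it.

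**The case for a change.** The best argument for acting is that this is the criterion that defines the population, that the defect is visible on the page, and that closing it would alter a few symbols. Screening is by chart review, and the randomization system asks only for confirmation that the patient is eligible, so no described step would catch an unscorable value. A calculator that awards points only when a row matches would exclude the patient with PT prolonged by 5.5 seconds in the example.

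Part of this stands. The PT gap does not depend on a symbol that might have been lost from the PDF. A lost equals sign in the platelet and fibrinogen rows cannot be ruled out, but such signs survive elsewhere in the same table. A few patients could be scored differently by two careful readers.

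The claimed harm does not stand. The calculator case is a programming fault that contradicts the table's own zero row, not a reading of the plan. Bands written as 3 to 5 and then 6 or more are what one would draft for whole seconds, although the document does not say that PT is so recorded. The counts of 17 and 24 are unweighted combinations, so 17 of 90 must not be read as a proportion of patients. The study has a single center, which limits variation between scorers, and the score is recalculated daily, so one boundary reading need not settle entry.

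**Conclusion.** The concern is right about the wording and wrong about the consequence. Exhibit 1 omits boundary detail that a sensible scorer supplies by using an adjacent row. On that reading the score is monotone in PT, and a PT in the gap affects entry only when D-dimer is normal. With moderate D-dimer, entry turns only on platelets or fibrinogen exactly at the boundary, with PT prolonged by less than 3 seconds. With D-dimer of 3.00 mcg/mL or more it never changes.

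Any inconsistency arises before allocation and cannot differ systematically between arms. The mortality comparison, its test and the 82 per arm stay as they are. What remains is slight blurring at the edge of the population. Its size in patients cannot be computed from the documents; that it is small is a judgement, resting on two of the gaps being single values and the third a one-second interval. The conclusion also assumes that scorers do not give zero points to a PT prolonged by more than 5 seconds. Tidying the table would be harmless housekeeping, but the soundness of the results does not depend on it.
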